## 3.4 Rescreening

Subjects who have failed the first screening can be re-screened (they must re-sign the ICF and be assigned a new screening number) at the discretion of the investigator. Subjects can be enrolled in the trial if they meet all the inclusion criteria specified in the protocol and do not meet any of the exclusion criteria at re-screening. Each subject is allowed to be re-screened once.

# 4. Overall Study Design

## 4.1 Study Type/Design

This study consists of a dose escalation trial and an expansion trial, both of which are designed as multi-center and open-label trials. This study aims to investigate the safety, tolerability, PK profiles and efficacy of BB102 tablets monotherapy (fasted or fed) orally administered at different doses in patients with advanced solid tumors and to evaluate the effect of food on the PK profiles.

# 4.1.1 Dose escalation trial (6 fasted dose escalation groups and 1 fed dose escalation group)

## 4.1.1.1 Basis for selection of starting dose

According to the International Conference on Harmonisation of Technical Requirements for Registration of Pharmaceuticals for Human Use (ICH)-S9 "Guideline on Nonclinical Evaluation for Anticancer Pharmaceuticals", a common approach for many small molecules anticancer drugs is to set a starting dose at 1/10 the STD10 in rodents of repeat-dose toxicity study; if the non-rodent is the most appropriate species, then 1/6 the HNSTD is considered an appropriate starting dose. According to the CDE "Technical Guidelines for Clinical Trials of Anticancer Drugs" and "Considerations for Starting Dose Calculation for Phase I Clinical Trial of New Anticancer Pharmaceuticals", in view of the ethical factors in tumor patients, 1/3 to 1/5 the no observed adverse effect level (NOAEL) is most commonly adopted for small molecule targeted anticancer pharmaceuticals. The corresponding human doses are calculated using the body surface area method based on the above parameters and nonclinical effective starting dose (see the following table). The female rat is the most sensitive species, and the corresponding maximum recommended starting dose (MRSD) is 107.4 mg/day based on the above parameters of nonclinical toxicology; the human equivalent dose calculated based on the nonclinical effective starting dose is 53.6 mg/day.

Nonclinical Toxicology							
Animal/study	Dosage (mg/kg/day)	Reference body weight of the subject (kg)	Safety factor	Calculation process	Alternative human MRSD (mg/day)		
Rats - 28 days QD - gavage - GLP	STD 10 : 300	60	10	300/36.88*6.60*60/10=322.1	322.1		
Beagle dogs - 28 days QD - gavage - GLP	HNSTD: Male 250;	60	6	250/36.88*21.47*60/6=1455.4; 100/36.88*21.47*60/6=582.2	Male 1455.4; Female 582.2;		

	Female 100 (deaths at high dose)						
Rats - 28 days QD - gavage - GLP	NOAEL: Male 300; Female 50;	60	5	300/36.88*6.60*60/5=644.3; 50/36.88*6.60*60/5=107.4	Male 644.3; Female 107.4;		
Beagle dogs - 28 days QD - gavage - GLP	NOAEL: Male 250; Female 40;	60	5	250/36.88*21.47*60/5=1746.5; 40/36.88*21.47*60/5=279.4	Male 1746.5; Female 279.4;		
Animal pharmacodynamic tumor model							
Animal/study	Effective dose (mg/kg)	Reference body weight of the subject (kg)	Safety factor	Calculation process	Human equivalent dose (mg/day)		
Nude mice - 21 days BID - oral	5	60	NA	5*2/36.88*3.29*60=53.6	53.6		

**Abbreviations:** BID = twice daily; GLP = Good Laboratory Practice; HNSTD = highest non-severely toxic dose; MRSD = maximum recommended starting dose; NOAEL = noobservedadverseeffect level; QD = once daily;  $STD_{10}$  = severely toxic dose to 10% of animals.

**Note:** The body surface area method is used for conversion, human dose (mg) = animal dose (mg/kg)  $\div$  (km human/km animal) \* 60 kg; km human = 36.88; km dog = 21.47; km rat = 6.60 (body weight 200 g); km mice = 3.29.

With the starting doses (e.g., 50, 60, 75, 140, 200, 300 mg/day), escalation doses (e.g., 50, 60, 75, 80, 100, 120, 150, 180, 200, 240, 250, 300, 320, 400, 450, 600, 800, 900, 1000, 1200, 1400, 1600, 2000, 2400 mg/day) and RP2D (e.g., 120, 600, 1000 mg/day) of similar drugs and strengths (10 mg, 50 mg) of BB102 tablets, this trial intends to use 50 mg as the starting dose.

#### 4.1.1.2 Rationale for selection of escalation doses

With a reference to the MTD of repeat-dose toxicity study (see the following table), MTD (e.g., 120 mg/day, 600 mg/day, MTD not reached) and RP2D (e.g., 120, 600 and 1000 mg/day) in the first-in-human study of similar drugs as well as the strengths (10 mg, 50 mg) of BB102 tablets, this study plans to adopt 420 mg as the maximum dose. Based on Fibonacci method, the proposed fasted escalation doses are: 50 mg QD, 100 mg QD, 160 mg QD, 240 mg QD, 320 mg QD and 420 mg QD.

#### **Nonclinical Toxicology**

Animal/study	MTD	Reference body weight of the subject (kg)	Calculation process	Human equivalent dose (mg/day)	1/2 human equivalent dose (mg/day)
Beagle dogs - long- term toxicity - 14 days QD - gavage - non-GLP	200 mg/kg/day	60	200/36.88*21.47 *60=6985.9	6985.9	3493.0
Rats - long-term toxicity - 14 days QD - gavage - non- GLP	300 mg/kg/day	60	300/36.88*6.60* 60=3221.3	3221.3	1610.6

Note: The body surface area method is used for conversion, human dose (mg) = animal dose (mg/kg)  $\div$  (km human/km animal) \* 60 kg; km human = 36.88; km dog = 21.47; km rat = 6.60 (weight 200 g).

Taking into account the human dose corresponding to the nonclinical effective starting dose (53.6 mg/day), the accelerated escalation (enrolling 1 subject only) of 50 mg enables quick escalation to the effective dose under the premise of guaranteeing the safety of subjects and subsequently avoids excessive exposure of subjects to ineffective doses.

In addition, according to the action mechanism of FGFR4 inhibitors, inhibition of FGF19/FGFR4 signaling pathway will upregulate CYP7A1 expression (CYP7A1 is associated with metabolism of bile acid) and subsequently cause an increase in bile acid secretion; bile acid secretion also increases after meal. Dose escalation trial of the similar drug FGF401 (NCT02325739) set up separate fed dose escalation groups. Therefore, in order to investigate the effect of food on the safety and tolerability (primary), PK profiles (secondary) of BB102 tablets monotherapy, in this study, an appropriate dose will be selected as the fed dose escalation group according to the previously obtained clinical trial data of BB102 tablets.

#### 4.1.1.3 Escalation method

This study adopts a modified 3+3 escalation design, including accelerated escalation and 3+3 escalation, with 6 fasted dose groups (50 mg QD, 100 mg QD, 160 mg QD, 240 mg QD, 320 mg QD and 420 mg QD) and 1 fed dose group. Note: Before the start of the dose escalation trial, the dosage of the fed dose group cannot be determined temporarily, and an appropriate dose will be selected subsequently by the safety monitoring committee (SMC) according to the previously obtained clinical trial data of BB102 tablets; the trial of the fed dose group can be synchronized with the dose escalation process of the fasted dose groups, and the trial of the fed dose group can also be started after the dose escalation of the fasted dose groups is completed, but the trial of the fed dose group must only be initiated after the equivalent dose is demonstrated to be safe under the fasted condition.

The starting dose group (50 mg QD group) is the accelerated escalation group; other dose groups are 3+3 escalation groups. See Figure 1. All subjects enrolled will firstly receive a single dose for safety observation and PK study, and then undergo a 5-day washout period. Later, subjects will receive multiple-dosing to continue the safety observation and PK study. Multiple-dosing is tentatively scheduled as: once daily in 21-day cycles. After Cycle 1 is finished, a subject can continue to receive the next cycle of treatment if the investigator believes that the subject may benefit from the study treatment.

[figure not shown]

Figure 1 The modified 3+3 escalation design in dose escalation trial

In order to avoid excessive exposure of subjects to ineffective doses, the accelerated escalation group (50 mg QD group) is planned to enroll 1 subject. The method for judging dose escalation is shown in Figure 2. During the DLT observation period (defined as the period from a single dose to the end of Cycle 1 of multiple-dosing), if there is no DLT or grade  $\geq$ 3 drug-related toxicity [defined as an adverse event (AE) definitely/possibly related to the study drug], the enrollment of the next dose group will be started; if any DLT or grade  $\geq$ 3 drug-related toxicity occurs, the group will be converted to the 3+3 escalation mode.

[figure not shown]

Figure 2 The accelerated escalation diagram in dose escalation trial

It is planned to enroll 3 subjects to other groups, and the specific dose escalation method is shown in Figure 3. For each dose group, if none of the 3 subjects experiences DLT, the trial will proceed

to the next dose group. If  $\geq 2$  out of the 3 subjects experience DLT, the dose escalation will be discontinued. If 1 of the 3 subjects experiences DLT, 3 additional subjects should be enrolled into this dose group (if none of the 3 newly enrolled subjects experiences DLT, the trial will proceed to the next dose group; If  $\geq 1$  of the 3 newly enrolled subjects experience DLT, dose escalation will be discontinued).

[figure not shown]

Figure 3 The 3+3 escalation diagram in dose escalation trial

The second and third subjects in the 3+3 escalation groups should only be enrolled after the first subject is observed for at least 5 days after dosing (enrolled on or after C1D1 of the first subject). If the previous subject experiences DLT, the sponsor and the investigator need to cautiously judge whether to enroll the next subject based on the safety data; if subsequent subjects have already been enrolled, the enrolled subjects should continue the study treatment (unless these subjects meet the criteria for study treatment discontinuation), with his/her safety data closely monitored.

SMC will decide whether to perform dose escalation or reduction and determine whether to and how to adjust the escalation doses based on the safety, tolerability and/or PK data obtained during the DLT observation period of a certain dose group. Based on the safety, tolerability, PK and efficacy data of a certain group, if the investigator believes that it is necessary to expand the number of subjects of this dose group to further observe the safety and efficacy and obtain PK data, the number of subjects of this dose group may be increased to 4-12 after reaching a consensus with the sponsor through discussion.

To ensure the safety of subjects, the washout time after single-dosing, dosing frequency, cycle setting, and time points of PK sample collection in the subsequent study as well as the design of subsequent escalation doses (e.g., adding dose groups of 520 mg QD and 600 mg QD) may be

timely adjusted based on the previously obtained safety, tolerability, PK parameters [e.g.,  $T_{1/2}$ , drug accumulation after multiple-dosing] and other previously obtained clinical trial data of BB102 tablets.

MTD is defined as the highest dose level in which DLT occurs in  $\leq 1/6$  of the total subjects during the DLT observation period. If MTD is not reached after administration of the maximum dose level shown above, the SMC will decide whether to increase dose groups based on the nonclinical data and the efficacy doses and PK parameters of domestic and foreign similar drugs observed in human.

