## 4.1.2 Expansion trial (expansion groups)

Based on the safety, tolerability, PK and efficacy data obtained in previous trials, 1 to 3 appropriate doses (e.g., 100 mg QD, 160 mg QD, and 240 mg QD) will be selected for the expansion trial.

The expansion trial can be initiated when the above doses are demonstrated to have a favorable safety in the dose escalation trial (i.e., the number of subjects experiencing DLT in the group is  $\leq 1/6$  of total subjects of the group), without waiting for the completion of the entire dose escalation trial.

Each expansion group will enroll 12 subjects to investigate the efficacy, safety and PK profiles of BB102 tablets. During the expansion trial, AEs meeting the definition of DLT will be regarded as AEs of special interest for safety assessment, thereby enriching the safety assessment data.

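### The ≤1/6 DLT criterion for the MTD and for opening expansion states no minimum number of subjects, so an MTD can be named on 0/3

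*Protocol*

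**What the plan says.** Section 4.1.1.3 (repeated in the Synopsis, item 1.2) gives the definition: "MTD is defined as the highest dose level in which DLT occurs in" at most 1/6 "of the total subjects during the DLT observation period". The next sentence deals with an MTD that has not been reached after the maximum dose level, and leaves the addition of dose groups to the safety monitoring committee (SMC).

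Section 4.1.2 (Synopsis, item 2) applies the same fraction to expansion: "The expansion trial can be initiated when the above doses are demonstrated to have a favorable safety in the dose escalation trial", explained as meaning that "the number of subjects experiencing DLT in the group is" at most 1/6 of the group. Expansion may open "without waiting for the completion of the entire dose escalation trial".

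Group sizes are also in section 4.1.1.3. For the start, "the accelerated escalation group (50 mg QD group) is planned to enroll 1 subject"; the other groups plan three. One DLT among three brings three more subjects. If two or more of the first three have a DLT, or one or more of the added three, escalation is discontinued. Separately, on the group's safety, tolerability, PK and efficacy data and by agreement of investigator and sponsor, "the number of subjects of this dose group may be increased to 4-12".

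Section 4.1.1.5 mentions a required minimum of DLT-evaluable subjects, but gives no number and serves only the replacement rule.

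**The concern.** The criterion is a bare proportion applied to groups that may hold anywhere from 1 to 12 subjects. At very small sizes a proportion of zero says little, yet the wording attaches the label MTD, or a demonstration of favourable safety, to it. The 3+3 rule judges a dose with one DLT only on six subjects. The MTD definition does not ask for six at the dose finally named, because nothing in the text goes back to fill the dose below a failed one.

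The MTD is a primary objective of the escalation trial (section 2.1) and feeds the choice of recommended phase II dose. The same fraction opens expansion groups of 12.

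The denominator is also loose. Sections 4.1.1.3 and 4.1.2 count total subjects, whereas sections 4.1.1.5 and 10.2 exclude from the DLT analysis those who received under 75% of the scheduled dose for reasons other than drug toxicity.

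**Working it through.** **Is an MTD on three subjects within the plan?** Section 10.1 expects 19-42 subjects in escalation. The lower bound is 1 (50 mg) + 5×3 (other fasted groups) + 3 (fed group) = 19; the upper bound is 7 groups × 6 = 42. So a full escalation with no dose above three subjects is planned for.

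**Which results meet ≤1/6 (16.7%)?**

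| Result | Rate | Meets ≤1/6 |
|---|---|---|
| 0/1 | 0% | yes |
| 0/3 | 0% | yes |
| 1/4 | 25% | no |
| 1/5 | 20% | no |
| 1/6 | 16.7% | yes |

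**How much does a clean small group show?** With no DLT in n subjects, the exact one-sided 95% upper limit is 1 − 0.05^(1/n):
- n = 1: 95%
- n = 3: 1 − 0.368 = 63%
- n = 6: 1 − 0.607 = 39%

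For 1/6 the exact upper limit is 58%.

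At an assumed true DLT rate of 33%, the chance of 0/3 is 0.67³ = 0.301. The 3+3 path lets such a dose pass with probability 0.67³ + 3×0.33×0.67²×0.67³ = 0.301 + 0.134 = 0.434, so 0.301/0.434 = 69% of those passes rest on 0/3 alone. Judged on six subjects with at most one DLT, the pass probability is 0.358.

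**What happens in a group enlarged after 0/3?** Assume a true rate of 10% and condition on 0/3. The chance that the dose then fails ≤1/6 is:
- n = 4 (one added): 0.10
- n = 5 (two added): 1 − 0.9² = 0.19
- n = 6 (three added, fails on two or more): 3×0.1²×0.9 + 0.1³ = 0.028

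One DLT in the fourth subject therefore removes the dose's status, and two further clean subjects restore it.

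**Do the two MTD sentences agree?** If escalation ends with 0/3 at 420 mg, then 420 mg is the highest dose level with DLT in at most 1/6, and so is the MTD by definition. The following sentence treats the MTD as possibly not reached at that point. The text does not say which reading governs, and 0/6 at 420 mg would raise the same conflict.

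**The case against.** Much of this is a property of any 3+3 design. The 63% limit applies to every cohort of three, and six subjects do not bring precision: 1/6 passes with an upper limit of 58%. That is right. The point is narrower: the label is stated without the evidence normally attached to it.

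The SMC decides on escalation, reduction and added dose groups (sections 4.1.1.3 and 4.1.1.6) and could ask for more subjects. It could, but no minimum binds it. Figures 1-3 are not visible in the text at hand; the prose describing them gives no minimum of six.

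Three stronger readings are tempting and are not supported:

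- **Groups of four or five arise routinely.** A reader might compute failure chances at a true 10% rate of 1 − 0.9⁴ = 34% and 1 − 0.9⁵ = 41%, against 11% for six. These treat the group size as fixed. Here one DLT among the first three leads to six subjects, so 1/4 or 1/5 is a final result only after 0/3, through the optional enlargement. The conditional figures of 10%, 19% and 2.8% apply.
- **An MTD on one subject is a likely result.** It needs 50 mg to clear on its single subject and 100 mg then to fail. The doses named as examples for expansion are 100, 160 and 240 mg.
- **Expansion should wait for six subjects.** Section 4.1.2 permits opening and does not compel it, selects doses on safety, tolerability, PK and efficacy data, and deliberately allows an early start. DLT-type events in expansion are followed as events of special interest. Early opening is a trade-off, not an error.

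**Conclusion.** The concern holds for the MTD definition. As written, an MTD may be declared on 0/3, with an upper limit of 63% and a 30% chance of that result at a true rate of 33%; 0/1 at 50 mg is an edge case. The wording also makes status depend on group size in a group enlarged after 0/3, and it conflicts with the sentence on an MTD not reached. For expansion the defect is one of description: a dose with 0/3 has not been demonstrated to be safe, but opening a group on it is permitted by design.

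The practical gain from asking for six is moderate. At a true 33% rate the pass probability falls from 0.434 to 0.358. The main benefit is that the reported MTD has a stated minimum of evidence behind it. The figures assume independent subjects with a common DLT rate at a dose; the 10% and 33% rates are illustrations, since the protocol gives none.

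**What to change.** - In section 4.1.1.3 and the Synopsis, state that the ≤1/6 criterion defines the MTD only when at least six DLT-evaluable subjects have been observed at that dose, and use DLT-evaluable subjects as the denominator, in line with sections 4.1.1.5 and 10.2.
- Where fewer than six are available, report the highest dose tested with its DLT count and exact upper confidence limit, and do not call it the MTD.
- Reconcile the definition with the sentence after it by saying what an MTD that is not reached means. The minimum of six does not settle this alone.
- In section 4.1.2, keep the early opening, but for a dose opened on fewer than six subjects report the count and upper limit instead of describing its safety as demonstrated.

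The change is a few sentences. It needs up to three more subjects at the dose named as MTD (6 − 3), or five at 50 mg (6 − 1). If that dose then fails, the question passes to the next lower dose on the same terms. The stated maximum of 42 = 7×6 has room for six in every group. The alternative cost is a less favourable label. No dose level and no DLT criterion changes.

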#### 4.1.1.4 DLT Definition

DLT observation period is defined as the period from a single dose to the end of Cycle 1 of multiple-dosing.

DLT is defined as an AE definitely/possibly related to the study drug occurring in the DLT observation period (AEs will be graded according to CTCAE v5.0) which meets any of the following criteria:

# (1) Hematologic toxicity

- 1) Grade 4 neutrophil count decreased for >3 days.
- 2) Grade 3 febrile neutropenia: ANC  $<1.0\times10^9$ /L with single temperature  $\ge 38.3^\circ$ C (101°F) or persistent temperature  $\ge 38^\circ$ C (100.4°F) for more than 1 hour.
- 3) Grade 4 PLT count decreased.
- 4) Grade 3 PLT count decreased with bleeding.
- 5) Grade 4 anemia.
- 6) Other grade 3 hematologic toxicities which do not recover to grade ≤2 after 7 days of symptomatic supportive treatment.

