#### (1) Hematologic toxicity

- 1) Grade 4 neutrophil count decreased for >3 days.
- 2) Grade 3 febrile neutropenia: absolute neutrophil count (ANC)  $<1.0\times10^9$ /L with single temperature  $\ge38.3^\circ$ C (101°F) or persistent temperature  $\ge38^\circ$ C (100.4°F) for more than 1 hour.
- 3) Grade 4 Platelet (PLT) count decreased.
- 4) Grade 3 PLT count decreased with bleeding.
- 5) Grade 4 anemia.
- 6) Other grade 3 hematologic toxicities which do not recover to grade  $\leq$ 2 after 7 days of symptomatic supportive treatment.

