#### (2) Non-hematologic toxicity

- 1) Grade ≥4 non-hematologic toxicity. Note: Toxicities with no safety risk at the discretion of the investigator are excepted, such as grade 4 GGT increased and alkaline phosphatase (ALP) increased.
- 2) Grade 3 non-hematologic toxicity (including but not limited to hepatobiliary disorders). Note: Toxicities with no safety risk at the discretion of the investigator (such as grade 3 nausea, vomiting, diarrhea, asthenia, constipation, loss of appetite, mucositis, GGT increased, ALP increased) are not defined as DLT, but they will be defined as DLT when the toxicities do not recover to grade ≤2 within 7 days under the circumstance of symptomatic supportive treatment are permitted.

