## (3) Other conditions

1) The grade is elevated from baseline with clinically significant and/or unacceptable toxicity, which is judged as a DLT by the SMC.

- 2) Drug discontinuation lasting 7 days or more due to drug-related toxicity.
- 3) The dose received by the subject during the DLT observation period is less than 75% of the scheduled dose due to toxicities attributable to study drug, and the investigator believes that it should be considered as a DLT.

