# In the dose escalation trial, dose interruption, resumption and permanent discontinuation during the DLT observation period:

- No dose adjustment is allowed in the DLT observation period, but the doses may be interrupted, resumed and permanently discontinued.
- ➤ If several toxicities occur at the same time, dose interruption, resumption and permanent discontinuation should be carried out according to the most serious toxicity.
- (1) During the DLT observation period, if the subject develops DLT, the doses should be interrupted, and supportive treatment should be given as needed. The doses can be continued when the dosage has been administered before dose interruption is more than 75% of the scheduled dose, and the subject recovers to grade  $\leq 1$  or baseline (or, recovers to grade  $\leq 2$  and the investigator believes that there is no safety risk).
- (2) If the subject develops DLT again, the doses should be permanently discontinued, and unscheduled safety follow-up should be arranged until the toxicity is resolved or stabilized.
- (3) If the subject has other non-DLT toxicities, dose interruption needs to be determined according to the investigator's medical assessment, and supportive treatment will be provided as needed.

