#### **Change in severity of AE:**

• If the patient experiences any changes in severity of AEs: (1) when the CTCAE grade is elevated, the AEs should be recorded separately, and the start date of the grade-elevated AE should be the same as the end date of the original AE; (2) when the CTCAE grade is reduced, the AE is not recorded separately, with only the highest CTCAE grade recorded, and the actions taken with the study drug and causal relationship with the study drug all remained as the records of the highest CTCAE grade, but the relevant information should

be updated in a timely manner, especially the outcomes and the end date.

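### Haematologic DLT item 6 counts an unrecovered other toxicity at grade 3 but names no counterpart at grade 4

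*Protocol*

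**What the plan says.** Section 4.1.1.4 makes a related adverse event in the DLT observation period a DLT if it meets any one listed criterion. The haematologic items are:

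- Item 1: grade 4 neutrophil decrease lasting more than 3 days.
- Item 2: "Grade 3 febrile neutropenia", defined by ANC and temperature thresholds.
- Items 3 and 4: grade 4 platelet decrease, or grade 3 with bleeding.
- Item 5: grade 4 anaemia.
- Item 6, the residual item: "Other grade 3 hematologic toxicities which do not recover to grade ≤2 after 7 days of symptomatic supportive treatment".

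Synopsis 1.3 has the same wording. The non-haematologic list begins instead with "Grade ≥4 non-hematologic toxicity", so its residual item has no upper limit.

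Three further clauses stand under other conditions:

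- a toxicity raised from baseline that the SMC judges to be a DLT;
- "Drug discontinuation lasting 7 days or more due to drug-related toxicity";
- "The dose received by the subject during the DLT observation period is less than 75% of the scheduled dose" because of drug toxicity, provided the investigator also considers it a DLT.

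On dosing within the DLT window, section 6.1.2 says "If the subject has other non-DLT toxicities, dose interruption needs to be determined" by the investigator's medical assessment.

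**The concern.** A toxicity definition should not treat a milder event more strictly than the same event at a higher grade. Item 6 does so for every haematologic toxicity without an item of its own. The haematology panel in 4.3.1 includes white cells and lymphocytes, and neither has a named DLT item. The protocol expects that such events can reach grade 4, because the dose-modification table in 6.1.2 has grade 4 rows under other haematologic toxicity.

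DLT is a primary endpoint of the escalation trial (7.1). It drives escalation and the MTD (4.1.1.3) and the opening of expansion (4.1.2). The same definition sets the adverse events of special interest in expansion (8.5). It is applied at each dose decision, so a statistical analysis plan cannot repair it afterwards.

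**Working it through.** No stated figure depends on this wording, so the check is one of coverage, followed by its effect on the 3+3 rule.

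**1. Coverage by the haematologic items, read literally**

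| Toxicity | Grade 3 | Grade 4 |
|---|---|---|
| Platelets | item 4 if bleeding | item 3 |
| Anaemia | item 6 if unrecovered at 7 days | item 5 |
| Febrile neutropenia | item 2 | outside the item 2 label, though its ANC and temperature test would usually be met; item 1 if grade 4 neutropenia exceeds 3 days |
| Any other haematologic toxicity | item 6 if unrecovered at 7 days | **none** |

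The authors write ≥ where they mean it: in the non-haematologic list, and in the 4.1.1.3 rule that any related grade ≥3 toxicity converts the 50 mg group to 3+3.

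**2. Remaining routes for an other grade 4 event**

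- SMC judgement: discretionary.
- Drug stopped for 7 days or more: automatic once it happens, but 6.1.2 leaves the interruption to the investigator.
- Less than 75% of scheduled dose: doses in the window are 1 (D1) + 21 (Cycle 1, once daily) = 22. Then 0.75 × 22 = 16.5, so at most 16 doses are taken and at least 22 − 16 = 6 are missed. Investigator agreement is also needed.

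A grade 4 event unrecovered at day 7, with dosing continued or with 5 or fewer doses missed, reaches neither dosing-based clause. At grade 3 the same event is a DLT under item 6.

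**3. Recording of grade changes (8.1.1)**

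The section says "when the CTCAE grade is elevated, the AEs should be recorded separately", and the grade 3 record closes when the new one opens. The text does not say whether item 6 still applies to an event that worsens before day 7. When the grade falls, only the highest grade is kept, so an event that drops from 4 to 3 and persists stays on record as grade 4.

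**4. Effect on the 3+3 rule**

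- 1/3 (add 3 subjects) becomes 0/3 (escalate).
- 2/6 = 0.33 (stop) becomes 1/6 = 0.17, within the MTD and expansion limit of 1/6.

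For scale only, with assumed rates because the documents give none, let *p* be the probability that a subject has a counted DLT:

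P(escalate) = (1−p)³ + 3p(1−p)² × (1−p)³

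| True DLT probability | All counted | 2 points uncounted | 5 points | 10 points |
|---|---|---|---|---|
| 25% | 0.60 | 0.64 | 0.71 | 0.81 |
| 33% | 0.43 | 0.47 | 0.54 | 0.64 |

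**The case against.** The strongest reply is that the gap is narrow. If the drug is held for a grade 4 event that has not recovered by day 7, the 7-day clause already makes it a DLT without judgement. That clause would also catch most drug-related deaths. If the event recovers during a shorter hold, item 6 would not count it at grade 3 either, so nothing is inverted. What remains is dosing continued through, or restarted on, an unrecovered grade 4 event. After the DLT window the protocol's own table interrupts dosing for grade 4 other haematologic toxicity. The SMC reviews the data before each escalation, and the 50 mg group has its extra trigger.

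Frequency is also likely to be low. Nonclinical adverse findings centre on the liver, and no haematologic finding in the 28-day rat study was considered adverse. White cell and lymphocyte decreases appeared in female rats at 300 mg/kg/day and reversed. The protocol converts that dose to 3221.3 mg/day, about 7.7 times the planned 420 mg maximum (3221.3 / 420).

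Finally, item 2 is mainly a label conflict, and the 8.1.1 recording rule does not itself define DLTs.

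All of this limits the size of the problem, but it does not remove it. Two of the three backstops are discretionary, and the third depends on an interruption that is the investigator's choice. The SMC is made up of the sponsor, the investigator, the CRO's medical monitor and other relevant personnel (4.1.1.6), and its judgement is being used to repair a fixed rule. The 50 mg trigger does not extend to the other dose groups.

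**Conclusion.** The concern holds. As written, an other haematologic toxicity unrecovered after 7 days is automatically a DLT at grade 3 and not at grade 4, unless dosing is stopped long enough or someone decides to count it. Grade ≥3 was probably intended.

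The consequence is limited to cases where dosing continues or restarts early and the SMC does not intervene. In such a case one event can change the escalation step or bring a dose within the MTD and expansion limit. No event rate is claimed, and the probabilities above rest on assumed rates. The item 6 limb carries the finding; the item 2 limb is a matter of consistent wording. The correction should be made because the rule governs a primary endpoint and costs almost nothing to put right.

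**What to change.** In 4.1.1.4 and in synopsis 1.3, replace grade 3 with grade ≥3 in haematologic item 6, keeping the 7-day recovery condition, and do the same in item 2 for febrile neutropenia. With item 6 so worded, an event that worsens from grade 3 to grade 4 before day 7 stays within it.

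Whether a life-threatening other grade 4 event should count at once, without the 7-day wait, is for the clinical team. The 6.1.2 table, used after the DLT window and in expansion, lets non-life-threatening grade 4 laboratory values resume at the original dose, so an immediate rule would need to be squared with it.

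The cost is two one-character edits in each of two places, with no change to planned subjects, procedures or timelines.
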